12.0 Statistical Considerations

12.1 Data Analysis

- *OGTT Dynamic Responses:* The glucose and insulin responses during the OGTT is defined as the area under the curve (AUC) created by plotting the entire sequence of glucose or insulin values and calculated using the trapezoidal rule.⁵⁵
- *HCG-stimulated Dynamic Responses:* The testosterone, androstenedione and 17-hydroxyprogesterone responses during the HCG-ST is defined as the area under the curve (AUC) created by plotting the entire sequence of each of these hormone values, and calculated using the trapezoidal rule.⁵⁶
- *Lipid-stimulated Responses:* Responses of the various inflammation markers from MNC or plasma will be defined as the difference between the maximum lipid-stimulated value and the baseline basal value. If baseline basal values exhibit considerable intersubject

variability, the percent (%) change will be calculated defined as follows: (maximum lipid-stimulated value – baseline basal value / baseline basal value) x 100.

- *Insulin Sensitivity:* The calculated fractional glucose disappearance per insulin concentration unit adjusted for insulin clearance will be determined during a FS-IVGTT as a measure of peripheral insulin sensitivity (S_I).

12.2 Power Analysis

We do not expect >20% dropout based on previous studies.^{19,20} Thus, we do not anticipate any substantial bias in the results. Based on the high cost of adding a patient, recruitment will continue until 90 pre- and post-evaluations are completed up to a maximum of 113 patients rather than increasing the overall sample size up front.

Aim 1: The primary outcome for Aim 1 is HCG-stimulated testosterone AUC. Our salsalate treatment preliminary data sample size (n=6) is too small to calculate power for the main outcome. As there are three groups (lean non-IR, lean IR, obese), the three contrasts of interest will be comparing the mean difference in HCG-stimulated testosterone AUC between the salsalate and placebo arms within each study group (i.e. salsalate-treated lean non-IR vs placebo lean non-IR, salsalate-treated lean IR vs placebo lean IR, and salsalate-treated obese vs placebo obese). To keep the familywise type I error at 0.05, we will use a Sidak adjustment and set $\alpha=0.017$ for each contrast for the primary outcome.

There are no previous studies in women with PCOS that address any of the outcome variables related to salsalate treatment. Thus, there is no pilot data of salsalate vs. placebo from which to base our power calculations. However, our preliminary baseline HCG-ST data revealed similar results in women with PCOS or controls regardless of BMI. The HCG-stimulated testosterone AUC (ng/dl x 96 hr) in women with PCOS (n=17) compared with ovulatory controls (n=16) revealed a mean (\pm SD) of 7370 ± 2481 vs. 3659 ± 959 ($p<0.0001$, effect size [ES] =1.8). Furthermore, previous data gathered in women with PCOS (n=12) evaluating HCG-stimulated testosterone AUC in response to treatment with an insulin sensitizer revealed a significant ($p<0.04$) decrease in the mean (\pm SD) from 4395 ± 1294 (pre) to 3288 ± 1259 (post).⁵⁷

Our preliminary data presented above revealed an ES of 1.8 for the mean change in the PCOS group vs. controls. We expect that the post-salsalate treatment HCG-stimulated testosterone AUC will be similar to controls. The proposed sample size of 90 patients (15 salsalate and 15 placebo for each study group), will provide 90% power to detect an ES ≥ 1.4 (80% power to detect an ES ≥ 1.24), based on a two-sided two-sample t-test at 1.7% significance to account for multiple comparisons which will yield similar power to our proposed GLM model with a Sidak adjustment to control type I error level. We used the pre- and post-treatment HCG-stimulated testosterone AUC data above136 to obtain a reasonable estimate for common SD of change for each treatment group. A post-treatment decrease of 30% ($7672 - 0.3(7672)$) in the salsalate-treated group and a post-placebo decrease of 10% ($7672 - 0.1(7672)$) in the placebo group with common standard deviation of 990 (assuming a correlation of 0.7 between pre/post measures) will yield an ES of 1.55. This analysis is indicative of adequate power to detect a difference in our primary outcome.

The secondary outcome for Aim 1 is insulin sensitivity (S_I). Our primary comparison will be change in S_I between the salsalate and placebo groups in insulin-resistant subjects (lean IR and obese) as we do not anticipate a change in lean non-IR subjects. Previous data gathered in another insulin resistant population (n=9) evaluating insulin sensitivity in response to salicylate

treatment revealed a significant ($p<0.04$) increase in the mean ($\pm SD$) insulin sensitivity from 4.0 ± 2.7 (pre) to 5.9 ± 1.8 (post).²³ These data indicate that a sample size of 30 subjects per group is sufficient to achieve 80% power to detect an ES ≥ 1.74 for salsalate vs. placebo based on a two-sided two-sample t-test at a 0.05 alpha level to account for multiple comparisons again yielding similar power to our GLM model.

This study is not powered to compare ovulation rates among the separate groups. Thus, ovulation rate post-treatment based on detection of luteal range progesterone elevations guided by BBTs will be compared between the salsalate and placebo groups overall. Based on the inclusion criteria, patients will be anovulatory pre-treatment, thus only post-treatment rates will be compared. With a sample size of 45 in each treatment group, if we expect approximately 10% to ovulate in the placebo arm, we will have over 80% power to detect a statistically significant difference if ovulation increases by 40% in the salsalate-treated group based on Fisher's exact test with type I error set at 0.05.

Aim 2: The primary outcome for Aim 2 is lipid-stimulated NF κ B EMSA density (i.e. change from baseline). The three contrasts of interest will be comparing the mean difference in lipid-stimulated NF κ B EMSA density between the salsalate and placebo group within each study group (i.e. salsalate-treated lean IR vs placebo lean IR, salsalate-treated lean non IR vs placebo lean non IR, and salsalate-treated obese vs placebo obese). Our preliminary baseline CCT data revealed similar results in women with PCOS and obese controls.¹¹ The lipid-stimulated NF κ B EMSA density in women with PCOS (n=17) compared with lean controls (n=8) revealed a mean ($\pm SD$) % change of 20.1 ± 10.4 vs. -3.0 ± 9.1 ($p<0.0001$, ES=1.9). The secondary outcomes for Aim 2 are glucose-stimulated NF κ B EMSA density and lipid-stimulated ROS generation (i.e. change from baseline). For women with PCOS compared with lean controls, our previously published baseline OGTT data showed a mean ($\pm SD$) % change of 34.6 ± 45.7 vs. -21.6 ± 35.6 ($p<0.04$, ES=1.4),¹³ and our baseline preliminary CCT data showed a mean ($\pm SD$) % change of 92 ± 38 vs. -7 ± 22 in ROS generation ($p<0.0001$, ES=3.8). For each of these outcomes, we will use a similar GLM framework as described in Aim 1 with the same three contrasts of interest. We will use a Sidak adjustment to control the type I error for each outcome. We expect post-salsalate treatment measures in PCOS will be similar to lean controls. Based on a two-sided two-sample t-test with a 0.017 α level to account for multiple comparisons which will yield similar power to our GLM model, we will have 80% power to detect an ES ≥ 1.24 . Thus, our study is sufficiently powered for these outcome measures.

Based on baseline PCOS vs. control data and using the approach described to analyze the primary and secondary outcomes, there is also 80% power to detect an ES ≥ 1.24 for lipid-stimulated p47 $^{\text{phox}}$ WB density (16.4 ± 10.9 vs. -6.4 ± 6.3 [$p<0.0001$, ES=2.6]) and lipid-stimulated MNC-derived TNF α release (8.4 ± 11.8 vs. -7.4 ± 9.4 [$p<0.008$, ES=1.5]). These 2 variables and those for which we lack preliminary data to estimate power; (i.e. salsalate-treated vs. placebo lipid- and glucose-stimulated p47 $^{\text{phox}}$, p65 NF κ B and TNF α mRNA content, and plasma CRP and TNF α) are exploratory outcomes key to providing means and SDs to plan larger studies.

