12.3 Statistical Analysis

Initially, a full descriptive analysis of the data will be performed. Frequency distributions will be computed for all raw data and for change from baseline responses to lipid or glucose stimulation. Summary statistics will be provided by treatment group (salsalate, placebo) overall as well as by treatment group and study group (lean non-IR, lean IR, obese).

- i. Baseline data such as age, BMI, androgens, insulin sensitivity, total body fat and visceral fat will be compared between groups (salsalate: lean non-IR, lean IR, obese; placebo: lean non-IR, lean IR, obese) using analysis of variance (ANOVA) for normally distributed data or Kruskal-Wallis test for non-normal data to validate similarity of characteristics within each study group across the 2 treatment arms. If there is statistical significance, multiple comparisons between groups will be performed using a Sidak adjustment.
- ii. The primary outcome for Aim 1 is a difference in HCG-stimulated testosterone AUC between salsalate vs. placebo. To test our hypothesis, we will use a GLM framework with a dependent variable of post-treatment HCG-stimulated testosterone AUC including covariates for pre-treatment HCG-stimulated testosterone AUC, treatment indicator, study group (lean non-IR, lean IR, obese) and the treatment by study group interaction. Of primary interest will be the three contrasts of difference in mean between salsalate vs. placebo for these study groups. A Sidak adjustment will be used to control the Type I error. Analysis for the secondary measure of difference in S_i between salsalate and placebo for the insulin-resistant subjects only (lean IR, obese) will be compared using the same GLM framework, although only the overall contrast of difference in means between salsalate and placebo is of interest. Assumptions and model fit will be checked for all primary and secondary outcome analyses. Data will be transformed if necessary.

Post-treatment ovulation rates based on ultrasound documentation of follicular collapse will be compared between the salsalate-treated group and the placebo group using Fisher's exact test with type I error at 0.05. Also, ovulation rates and 95% exact confidence intervals will be estimated by study group (lean with IR, lean without IR, and obese) and treatment group.

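### The Aim 1 power example divides an effect scaled to a mean of 7672 by an SD from a study with mean 4395; matched inputs give an effect size of 0.77 to 0.98, not 1.55

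*Combined protocol and SAP*

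**What the plan says.** Section 12.2 (Aim 1) plans three salsalate-versus-placebo contrasts, each with 15 women per arm at a two-sided level of 0.017. It gives the detectable effect size (ES) as 1.24 at 80% power and 1.4 at 90%.

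It cites two data sets for the HCG-stimulated testosterone AUC:
- the sponsor's baseline data, PCOS (n=17) against ovulatory controls (n=16): "7370 ± 2481 vs. 3659 ± 959";
- an insulin-sensitizer study in PCOS (n=12), with 4395 ± 1294 before and 3288 ± 1259 after treatment.

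Pre/post data given earlier in the section are used "to obtain a reasonable estimate for common SD of change for each treatment group". The worked example then takes a 30% fall on salsalate and a 10% fall on placebo, both from 7672, "with common standard deviation of 990 (assuming a correlation of 0.7 between pre/post measures) will yield an ES of 1.55". The next sentence concludes: "This analysis is indicative of adequate power to detect a difference in our primary outcome".

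The section also states an expectation: "We expect that the post-salsalate treatment HCG-stimulated testosterone AUC will be similar to controls". Section 12.3 specifies a model for post-treatment AUC "including covariates for pre-treatment HCG-stimulated testosterone AUC, treatment indicator", study group and their interaction.

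**The concern.** The numerator of the 1.55 is 20% of 7672. The denominator belongs to women whose baseline mean was 4395. In the one sample the documents give near 7672, the cross-sectional SD is 2481, about twice the 1294 behind the 990. Pairing the larger mean with the smaller SD inflates the effect size.

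This matters because the 30%-versus-10% case is the only treatment comparison behind the claim of adequate power for this outcome. The other effect size quoted, 1.8, compares untreated PCOS with controls. Someone interpreting a null contrast would believe the trial had about 95% power for a 20-point difference in percentage fall.

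**Working it through.** **Inputs.** All are from Section 12.2: 15 per arm, two-sided alpha 0.017, r = 0.7, a difference of 20% of the baseline mean, and the means and SDs above. Power is from the noncentral t. The lower figure of each range uses 28 df (two-sample t-test). The upper uses the residual df of the six-cell model: 90 − 6 = 84 for change, 83 with the baseline covariate.

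**Reproducing the plan.**
- SD of change = √(1294² + 1259² − 2 × 0.7 × 1294 × 1259) = 989, which is the plan's 990. This identifies the insulin-sensitizer study as the source.
- 0.2 × 7672 = 1534.4, and 1534.4 / 990 = 1.55. Power is 95–96%.
- Detectable ES at 28 df: 1.243 (80%) and 1.413 (90%), in agreement with the plan.

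**Which input drives the error.** The mean 7672 appears nowhere else, but replacing it with 7370 changes little: 1474 / 990 = 1.49. The SD is what matters. At r = 0.7, a change SD of 990 implies a cross-sectional SD of 990 / √0.6 = 1278, or 17% of 7672. The two sources have 34% (2481/7370) and 29% (1294/4395).

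**Mean and SD from the same source, r = 0.7.** For change from baseline in the 7370 sample, SD = 2481 × √(2 − 2 × 0.7) = 1922. For the baseline-adjusted model, residual SD = SD × √(1 − 0.7²), using 2481 or the post-treatment 1259.

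| Source | Analysis | Difference | SD | ES | Power |
|---|---|---|---|---|---|
| 7370 ± 2481 | change | 1474 | 1922 | 0.77 | 35–37% |
| 7370 ± 2481 | adjusted | 1474 | 1772 | 0.83 | 41–44% |
| 4395 study | change | 879 | 989 | 0.89 | 47–50% |
| 4395 study | adjusted | 879 | 899 | 0.98 | 56–60% |

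A simulation of the six-cell model gave 44% (7370) and 59% (4395) for the adjusted rows.

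**Sensitivity to r** (change and adjusted analyses together).

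| r | 7370 source | 4395 source |
|---|---|---|
| 0.5 | 20–30% | 27–41% |
| 0.7 | 35–44% | 47–60% |
| 0.9 | 86–90% | 95–97% |

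Reaching ES 1.24 needs r of about 0.88–0.89 (7370) or 0.83–0.85 (4395).

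**Control-level expectation.** If salsalate reaches 3659 and placebo falls 10%, the difference is 0.9 × 7370 − 3659 = 2974. With SD 2481 in both arms and r = 0.7, ES is 2974/1922 = 1.55 (change) or 2974/1772 = 1.68 (adjusted), with power 95–98%. At r = 0.5 power is 77–91%.

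**The case against.** - **It is a choice of SD, not an arithmetic slip.** True: 1.55 follows from the stated inputs, and the plan does not name the SD's source outright. But the 989 reproduces exactly from the only pre/post testosterone data given.
- **A constant SD is itself an assumption.** The effects are percentages, SD rises with the mean across the samples cited, and Section 12.3 allows transformation. If post-treatment SDs shrank to 0.7 and 0.9 of 2481, the adjusted residual SD would be 2481 × √(0.51 × (0.49 + 0.81)/2) = 1428 and ES 1.03. On a log scale with baseline coefficients of variation, ES is 0.99–1.07 (7370) or 1.13–1.22 (4395). The last value gives 78–82% power, but falls to an ES of about 0.95 with that study's post-treatment coefficient of variation. So 0.77–0.98 depends on the model. However, the plan states a common SD, the sensitizer study's SD hardly moved (1294 to 1259), and no alternative comes near 1.55.
- **The documents report a larger salsalate effect.** Section 2.0 gives a 44% reduction in ovarian androgen secretion in lean insulin-sensitive women. Against a 10% placebo fall at r = 0.7, that yields ES 1.30–1.41 (7370) or 1.51–1.66 (4395), all above 1.24. This stands as a reason not to call the trial underpowered. It does not repair the 30% example, and Section 12.2 itself calls its salsalate preliminary data (n=6) too small for a power calculation.
- **Everything depends on r, for which no data are given.** This stands, and is why a range should be shown rather than one replacement figure.
- **The control-level calculation also assumes a common SD**, although the controls' SD is 959. With 959 after salsalate the change ES stays about 1.54; the assumption should be named.

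**Conclusion.** The concern holds. With the plan's own r = 0.7 and common-SD assumption, and mean and SD from one source, the 30%-versus-10% example gives an ES of 0.77 to 0.98 and 35–60% power per contrast, not 1.55 and 95–96%. It does not support the claim of adequate power that follows it. A correlation near 0.9 would restore power.

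The detectable effect sizes of 1.24 and 1.4 are correct. The control-level expectation keeps 95–98% power at r = 0.7. What fails is the stated justification; a shortfall for every effect the plan anticipates is not shown. It should be fixed because it is the power figure on which a reader would rely when interpreting the three primary contrasts.

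**What to change.** Change only the Aim 1 example in Section 12.2:

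1. Use one sourced baseline mean with an SD on the same scale; drop 7672 or give its source.
2. Restate the example, for instance: *With baseline 7370 ± 2481, a common SD and r = 0.7, falls of 30% and 10% (difference 1474) give an ES of 0.77 for change (SD 1922) and 0.83 for the baseline-adjusted model (residual SD 1772), that is 35–44% power per contrast at the 1.7% level. Power is 20–30% at r = 0.5 and 86–90% at r = 0.9.*
3. Remove the sentence on adequate power, or rest it on the control-level expectation and show the calculation: *If salsalate reaches the control mean of 3659 and placebo falls 10% (difference 2974), with SD 2481 assumed in both arms, the ES is 1.55–1.68 and power 95–98% at r = 0.7 (77–91% at r = 0.5).*

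The cost is wording and a less favourable stated power for the 30%-versus-10% case. Enrolment, the three contrasts, the Sidak level and the model are unchanged, and no analysis is added.

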12.3 Statistical Analysis

Initially, a full descriptive analysis of the data will be performed. Frequency distributions will be computed for all raw data and for change from baseline responses to lipid or glucose stimulation. Summary statistics will be provided by treatment group (salsalate, placebo) overall as well as by treatment group and study group (lean non-IR, lean IR, obese).

- i. Baseline data such as age, BMI, androgens, insulin sensitivity, total body fat and visceral fat will be compared between groups (salsalate: lean non-IR, lean IR, obese; placebo: lean non-IR, lean IR, obese) using analysis of variance (ANOVA) for normally distributed data or Kruskal-Wallis test for non-normal data to validate similarity of characteristics within each study group across the 2 treatment arms. If there is statistical significance, multiple comparisons between groups will be performed using a Sidak adjustment.
- ii. The primary outcome for Aim 1 is a difference in HCG-stimulated testosterone AUC between salsalate vs. placebo. To test our hypothesis, we will use a GLM framework with a dependent variable of post-treatment HCG-stimulated testosterone AUC including covariates for pre-treatment HCG-stimulated testosterone AUC, treatment indicator, study group (lean non-IR, lean IR, obese) and the treatment by study group interaction. Of primary interest will be the three contrasts of difference in mean between salsalate vs. placebo for these study groups. A Sidak adjustment will be used to control the Type I error. Analysis for the secondary measure of difference in S_i between salsalate and placebo for the insulin-resistant subjects only (lean IR, obese) will be compared using the same GLM framework, although only the overall contrast of difference in means between salsalate and placebo is of interest. Assumptions and model fit will be checked for all primary and secondary outcome analyses. Data will be transformed if necessary.

Post-treatment ovulation rates based on ultrasound documentation of follicular collapse will be compared between the salsalate-treated group and the placebo group using Fisher's exact test with type I error at 0.05. Also, ovulation rates and 95% exact confidence intervals will be estimated by study group (lean with IR, lean without IR, and obese) and treatment group.

- iii. Aim 2 will evaluate lipid-stimulated NF κ B EMSA density (primary outcome), glucose-stimulated NF κ B EMSA density and lipid-stimulated ROS generation (secondary outcomes) along with the exploratory variables described in the power analysis. Primary and secondary outcomes will be transformed (e.g. logarithmic transformation) if either measure is not normally distributed and will be analyzed using a GLM framework as described for Aim 1 to compare salsalate vs. placebo for each study group. A Sidak adjustment will be used to control type I error. Descriptive statistics will be provided for exploratory variables.

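### Testing the three within-group contrasts with a Holm-Sidak step-down, in place of a fixed Sidak level of 0.017, would add power at the same 5% familywise error

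*Combined protocol and SAP*

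**What the plan says.** Section 12.2 (Power Analysis, Aim 1) of the combined protocol and SAP sets the error target and the level: "To keep the familywise type I error at 0.05", and then "we will use a Sidak adjustment and set $\alpha=0.017$ for each contrast for the primary outcome". Section 12.3, item ii, defines the tests: "Of primary interest will be the three contrasts of difference in mean between salsalate vs. placebo for these study groups". The sentence that follows is "A Sidak adjustment will be used to control the Type I error". The cells are small: "The proposed sample size of 90 patients (15 salsalate and 15 placebo for each study group".

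Aim 2 uses the same three contrasts. Section 12.2 says "We will use a Sidak adjustment to control the type I error for each outcome", and 12.3, item iii, says "A Sidak adjustment will be used to control type I error". The Aim 2 power statement also uses 0.017.

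Section 12.3 does not itself say whether the adjustment is single-step or stepwise. The fixed 0.017 for each contrast in 12.2 settles that it is single-step. Neither section mentions a step-down, ordered or closed procedure.

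**The concern.** Under a single-step rule each contrast must reach 0.017 whatever the other two show. A step-down rule relaxes the level for the remaining contrasts once one has been rejected, without raising familywise error. The single-step rule therefore gives away power on the second and third rejections.

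Those rejections matter here. The hypotheses in section 3.0 expect salsalate to act in every study group, irrespective of body composition and insulin resistance, and that is the setting in which the step-down gains most. There are only 15 women per arm in each group, and section 12.2 cites the cost of each added patient as a reason not to enlarge the sample up front. This gain needs no extra patients.

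**Working it through.** **Inputs.** From 12.2 and 12.3: familywise error 0.05; three contrasts in separate patients; 15 versus 15 in each group; two-sided two-sample t-test (28 df); detectable effect sizes (ES) 1.24 (80% power) and 1.4 (90%); projected Aim 1 ES 1.55; ES 1.9 for the Aim 2 primary outcome, being the stated PCOS-versus-lean-control difference that salsalate is expected to remove.

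**The plan's own figures.** The Sidak level is 1 − 0.95^(1/3) = 0.01695, which rounds to 0.017. The noncentral t with noncentrality ES × √(15/2) gives 79.8% power at ES 1.24 (stated 80%) and 89.4% at ES 1.4 (stated 90%). The projected effect is 0.2 × 7672 / 990 = 1.55. All reproduce.

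**Step-down levels.** Smallest p at 1 − 0.95^(1/3) = 0.01695; next at 1 − 0.95^(1/2) = 0.02532; last at 0.05; stop at the first failure. The first level equals the single-step level and the later ones are larger, so no single-step rejection is lost.

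**Error control.** With m true nulls, a false rejection requires the smallest of the m null p-values to be at or below 1 − 0.95^(1/m). For independent tests that has probability 1 − (0.95^(1/m))^m = 5%. Exact values for three independent t-tests, with ES 1.24 in any group that responds, are 5.0% (three nulls), 4.7% (two) and 4.2% (one). The planned GLM shares an error variance and a baseline slope across contrasts. Simulating it (40,000 runs, pre/post correlation 0.7) gave 5.03%, 4.8% and 4.7%, with Monte Carlo error of about 0.1 point.

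**Power at ES 1.24 in all three groups.** Let A, B and C be the power at 0.01695, 0.02532 and 0.05: A = 0.7977, B = 0.8427, C = 0.9061.

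- Per contrast, single-step: A = 79.8%.
- Per contrast, step-down: A + (B − A)[1 − (1 − A)²] + (C − B)[B² − (B − A)²] = 0.7977 + 0.0432 + 0.0449 = 88.6%.
- All three, single-step: A³ = 50.7%.
- All three, step-down: A³ + 3A²(C − A) + 3A(B − A)² + 6A(B − A)(C − B) = 0.5075 + 0.2069 + 0.0048 + 0.0137 = 73.3%.
- At least one, either rule: 1 − (1 − A)³ = 99.2%.

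**Other effect sizes, equal in all groups (28 df).**

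| ES | Role in the plan | Per contrast | All three |
|---|---|---|---|
| 1.24 | detectable, 80% power | 79.8% → 88.6% | 50.7% → 73.3% |
| 1.4 | detectable, 90% power | 89.4% → 95.3% | 71.4% → 87.8% |
| 1.55 | projected, Aim 1 | 94.9% → 98.2% | 85.5% → 95.1% |
| 1.9 | Aim 2 primary, as stated | 99.4% → 99.9% | 98.3% → 99.7% |

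**Unequal effects (ES 1.24 where a group responds, 28 df).** Two groups respond: 79.8% → 83.5% for each. One responds: 79.8% → 79.9%. One group at half effect (0.62) with the other two at 1.24: that group goes from 22% to 34%, or from 24% to 36% with a pooled error on 83 df.

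**Closer to the planned model.** With pooled error (90 − 7 parameters = 83 df) and ES 1.24 throughout, per-contrast power goes from 83% to 90% and all-three power from 58% to 77%. In the simulated baseline-adjusted GLM, with ES 1.24 on the change-score scale, the figures are 88.7% → 94.5% and 70.1% → 85.8%.

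**The case against.** Single-step Sidak does exactly what section 12.2 sets out to do, and no conclusion drawn under it would be invalid. This is a choice between two valid procedures. That stands.

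The largest gains occur at ES 1.24, which is a detectable threshold and not what the plan expects. At its projected 1.55 the gain is about 3 points per contrast, at 1.9 it is under 1 point, and baseline adjustment shrinks it further. That also stands. The counterweight is that section 12.2 says there are no salsalate-versus-placebo pilot data, so a true effect nearer 1.24 cannot be excluded.

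A reader might infer that the trial has only a 51% chance of success. The documents do not support this. They speak of three contrasts of interest under familywise control, do not call them co-primary, and nowhere require all three to be significant. The all-three figure is relevant to the section 3.0 hypothesis but is not a decision rule of the plan.

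Finally, single-step Sidak has simple matching simultaneous intervals and a step-down does not. That is true, but the plan specifies no intervals for these contrasts; the only ones in 12.3 are exact intervals for ovulation rates.

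**Conclusion.** The point holds as an inexpensive gain in efficiency. It is not an error in the plan: error control is sound and the stated power is right. If all three groups respond equally, the step-down adds 8.8 points per contrast at ES 1.24, 5.9 at 1.4, 3.3 at 1.55 and under 1 at 1.9. For all three contrasts together it adds 22.6, 16.4, 9.6 and 1.4 points. The gain is about 4 points per contrast if two groups respond and negligible if one does, and the chance of at least one rejection never changes.

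These figures assume 15 completers per cell, normal outcomes with a common variance, and independent contrasts. The direction is the same under the planned GLM. It would be too strong to say that power is the limiting resource for both primary outcomes, because at the plan's own expected effects power per contrast is already about 95% or more.

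**What to change.** Before unblinding, in section 12.2 and in 12.3 (items ii and iii), replace the fixed 0.017 for each contrast with a Holm-Sidak step-down at familywise 0.05 over the three contrasts. Apply it separately to each outcome now Sidak-adjusted over those contrasts: HCG-stimulated testosterone AUC, lipid-stimulated and glucose-stimulated NFκB EMSA density, and lipid-stimulated ROS generation. Report adjusted p-values. Keep the stated 80% and 90% figures, described as conservative power at the first step.

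If simultaneous intervals are wanted, add single-step Sidak intervals and note that one may include zero when the step-down test rejects. That possible mismatch is the only real downside. The cost is about a sentence of wording in each place, with no change to sample size, data collection or the error target.

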6.0 Study Design and Procedures

This research will involve the prospective study of 90 reproductive age women (18-40 years) with PCOS using a randomized double-blind placebo-controlled study design. The randomization schedule will be stratified by body mass index (BMI) (lean: BMI ≥ 18 but ≤ 25 kg/m²; obese: BMI ≥ 30 but ≤ 40 kg/m²) and IR status study groups to ensure a balance of patients in the two study arms. IR will be defined by the insulin area under the curve from 0-120 min (insulin AUC₀₋₁₂₀) of an oral glucose tolerance test (OGTT) $> 7,000$ which is highly predictive and thus, recommended for population assessment of IR in PCOS.³⁵ Forty five (45) of the women with PCOS will receive salsalate of which 30 will be lean (15 without IR; 15 with IR) and 15 will be obese. The other 45 women with PCOS with a similar frequency distribution of BMI and IR status will receive placebo. Thus, the study will be comprised of the following 6 groups:

1. Salsalate-treated lean PCOS without IR (n=15)
 - BMI ≤ 25 kg/m² – and – 2-hour oral glucose tolerance test (OGTT) insulin area under the curve (AUC) $\leq 7,000$
2. Placebo-treated lean PCOS without IR (n=15)
 - BMI ≤ 25 kg/m² – and – 2-hour OGTT insulin AUC $\leq 7,000$
3. Salsalate-treated lean PCOS with IR (n=15)
 - BMI ≤ 25 kg/m² – and – 2-hour OGTT insulin AUC $> 7,000$
4. Placebo-treated lean PCOS with IR (n=15)
 - BMI ≤ 25 kg/m² – and – 2-hour OGTT insulin AUC $> 7,000$
5. Salsalate-treated Obese PCOS – BMI ≥ 30 kg/m² – ≤ 40 kg/m² (n=15)
6. Placebo-treated Obese PCOS – BMI ≥ 30 kg/m² – ≤ 40 kg/m² (n=15)

After the initial pre-screening, volunteers will be asked to come to the CCTS CRC at [name] for a screening visit at ~ 8:00 AM. The screening visit will occur within 1 to 4 weeks of beginning the study protocol and will last ~4 hours. At the start of the screening visit, volunteers will undergo informed consent followed by a complete history and physical, vaginal sonography, and blood draws for a hormonal evaluation if not performed previously, a complete blood count (CBC), a comprehensive metabolic panel (CMP) and an OGTT. Based on the screening results, volunteers deemed eligible for study participation will subsequently enter the study protocol beginning between days 3 and 13 following the onset of either a spontaneous or progestin-induced withdrawal bleed, or without regard to the onset of menses if vaginal

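### The S_I analysis set is called insulin-resistant, but its obese half is not selected by the plan's own insulin criterion, so its result is not by definition a result in IR women

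*Combined protocol and SAP*

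**What the plan says.** Section 6.0 gives one definition: "IR will be defined by the insulin area under the curve from 0-120 min" of the OGTT, with a cut-off above 7,000. The group list that follows applies this cut-off to the four lean groups. The two obese groups carry a BMI range and nothing else: "Salsalate-treated Obese PCOS – BMI ≥ 30 kg/m² – ≤ 40 kg/m² (n=15") and "Placebo-treated Obese PCOS – BMI ≥ 30 kg/m² – ≤ 40 kg/m² (n=15").

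Section 12.2 places the S_I comparison "in insulin-resistant subjects (lean IR and obese"), and leaves out lean non-IR women because no change is expected in them. Section 12.3, item ii, repeats the set "for the insulin-resistant subjects only (lean IR, obese"), and makes a single overall salsalate-versus-placebo contrast the one of interest.

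Section 3.0 frames the S_I part of Aim 1 as an expected improvement in women with IR. Section 6.1 plans the screening OGTT partly to establish IR status and does not confine it to lean volunteers. The documents nowhere state that all obese women are taken to be insulin resistant, and they give no IR rate for obese women.

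**The concern.** The label and the selection rule do not match. By the Section 6.0 definition, an obese woman with an AUC of 7,000 or less is not insulin resistant, yet she enters an analysis described as restricted to insulin-resistant women. Section 12.2 excludes lean non-IR women because no change is expected in them; if that reasoning extends to obese women, she does not belong in the set either.

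Two things are at stake. The first is the target population: a result from this set cannot be reported, on the plan's own terms, as an effect in IR women. This matters in a trial whose overarching hypothesis treats adiposity and IR as separate factors. The second is power: any obese women who are non-IR and respond less would pull the pooled contrast toward zero. Because only the overall contrast is planned, no planned S_I test would show whether the two halves differ.

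**Working it through.** **Composition of the set.** Section 6.0 gives 15 lean IR and 15 obese women per arm, so 30 per arm and 60 in all. Half of them (15/30 per arm) have no insulin criterion. Recruitment continues until 90 women complete (Section 12.2), so 30 per arm is kept here.

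**The plan's own figure.** Section 12.2 states that 30 per group gives 80% power for an effect size (ES) of at least 1.74, with a two-sided two-sample t-test at alpha 0.05. Solving the noncentral t power function for these inputs gives ES = 0.736, which rounds to 0.74. As a check, the normal approximation is (1.96 + 0.84) × √(2/30) ≈ 0.72. At ES = 1.74 with 30 per arm, power exceeds 99.9%. The printed 1.74 is therefore not reproduced. It may be a slip for 0.74, but the documents do not settle that, so both are carried below.

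**Dilution formula.** Let d be the standardised effect in IR women and f the share of obese women with AUC at or below 7,000. Assume no effect in those women. With half the weight on each group:

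- Overall effect in the planned set = ½·d + ½·(1 − f)·d = d(1 − f/2), with 30 per arm.
- Effect in the AUC-defined set = d, with 30 − 15f per arm on average.

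Example at f = 20%: the planned set has 0.736 × 0.90 = 0.662 with 30 per arm; the AUC-defined set has 0.736 with 30 − 3 = 27 per arm.

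**Power, planned set versus AUC-defined set** (two-sided alpha 0.05; the column headed 0.74 uses the unrounded 0.736):

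| f | AUC-defined n per arm | d = 0.74 | d = 1.0 | d = 1.74 |
|---|---|---|---|---|
| 0 | 30 | 80 vs 80% | 97 vs 97% | both above 99% |
| 10% | 28.5 | 76 vs 78% | 95 vs 96% | both above 99% |
| 20% | 27 | 71 vs 76% | 93 vs 95% | both above 99% |
| 30% | 25.5 | 66 vs 73% | 90 vs 94% | both above 99% |
| 40% | 24 | 61 vs 70% | 86 vs 92% | both above 99% |

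The relevant cost is the gap between the two sets, not the fall from 80%, because the AUC-defined set also loses women. At d = 0.74 the gap runs from about 2 points (f = 10%) to about 9 points (f = 40%). At d = 1.0 it is about 1 to 6 points.

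**What the inputs rest on.** f is an assumption throughout. The only non-IR prevalence in the documents, 30-50% in Section 1.0, is for lean women. Zero effect in obese non-IR women is also an assumption, since Section 12.2 states that expectation for lean non-IR women only. The calculation ignores any gain from baseline adjustment and any extra variance from mixing responders and non-responders.

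**The case against.** A reader might infer that the S_I effect *is* diluted. The documents do not support that. Dilution needs some obese women at or below 7,000 and a smaller response in them, and neither is documented. If every obese woman exceeds 7,000, the two sets are identical and the label is true in practice.

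A reader might also infer bias between arms. That is not supported either. Women are randomised within study groups, so the contrast is sound for the set analysed.

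A third tempting reading is that the S_I analysis is underpowered. Starting from exactly 80% makes any loss look like a shortfall, but 0.74 is a detectable effect, not a forecast. The reference data in Section 12.2 (4.0 ± 2.7 before, 5.9 ± 1.8 after) give 1.9/2.29 = 0.83 on the pooled SD, √((2.7² + 1.8²)/2) = 2.29, if placebo is assumed not to change. At 0.83 the planned set has 85%, 81%, 77% and 72% power for f = 10% to 40%. At the printed 1.74 the question of power disappears.

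Finally, both statistical sections spell out in parentheses who is in the set, so nothing is hidden, and Section 12.3, item i, compares baseline insulin sensitivity across the six groups. That would show how insulin resistant the obese groups are on average. It would not give the number at or below 7,000.

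All of this limits the size of the point. None of it removes the mismatch between the label and the plan's own definition.

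**Conclusion.** The point holds as one of naming and target population on a secondary outcome. Half of the set described as insulin resistant is not selected by the plan's IR criterion, so the Aim 1 expectation about IR women is not tested in a set defined that way.

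Dilution is possible but not established. Its size depends on two unknowns, f and the effect in obese non-IR women, and on which effect size is realistic. Under zero effect and f of 10% to 40%, an AUC-defined set would gain about 2 to 9 points of power at 0.74 and practically nothing at 1.74. The discrepancy between 1.74 and 0.74 should be resolved, because it decides whether the power side of this point matters. The point about the label stands whichever figure is right.

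**What to change.** 1. In Sections 12.2 and 12.3, and in any conclusion, call the planned set *lean IR and obese*.
2. Prespecify the same baseline-adjusted S_I contrast in all women of that set whose screening insulin AUC 0-120 exceeds 7,000, and base any statement about IR women on it. The criterion is measured before randomisation, so this remains a comparison of randomised women. Arm sizes within the obese part may be uneven, because the obese groups are not divided by AUC.
3. State before unblinding which of the two S_I contrasts is the secondary test and which is supportive, so that the population is not chosen after the results are seen.
4. Report the number of obese women at or below 7,000 by arm.
5. Check the 1.74 in Section 12.2 against its stated inputs.

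The cost is a change of wording and one further model on data already planned at screening. The downside is that the AUC-defined set may be smaller (24 per arm at f = 40%) and that a second S_I result has to be reported and ranked.
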